# **Inclusion of B-ALL patients**

At any DL  $\geq$ 3, patients with B-ALL (see inclusion criterion I 01) may also be recruited in the Dose Escalation Part.

Property of the Sanofi Group - strictly confidential

Page 56

# **Study continuation**

The duration of each cycle of treatment is 42 days, with weekly administration of IMP (except for Cycle 1 Week 1 in DL  $\geq$ 3 when 2 administrations will be given).

The criteria for retreatment of patients are described in Section 6.5.

The dose given in the second or subsequent cycles will be the last dose given in the previous cycle. If there is a  $\geq$ 10-day interval between administrations of SAR440234, the next infusion must start with the lead-in doses appropriate for the selected dose level.

Additional pharmacokinetic data, safety and disease response will be assessed as indicated in the flow charts (Section 1.2) and when clinically indicated.

A Study Committee including the main Investigators, Sponsor's clinical team, and ad hoc experts, when appropriate, will regularly review the safety data, and will make recommendations as appropriate. The Study Committee will also decide the RP2D, including the recommended lead-in dose and schedule, for the Expansion Part in R/R AML and HR-MDS patients.

Additional (optional) cohort(s) beyond DL8, or intermediate dose levels, may be evaluated; the decision to proceed with these optional cohort(s), however, will be discussed with the Study Committee and will be based on the available safety, exploratory, and pharmacokinetic data.

It is anticipated that the number of patients enrolled in the Dose Escalation Part will be 30 to 40.

### 6.3 MAXIMUM ADMINISTERED DOSE / MAXIMUM TOLERATED DOSE

The dose escalation will end when the MAD is reached, which will be defined as the dose at which ≥33% of evaluable patients have experienced an IMP-related DLT during the DLT observation period in a cohort of 6 patients.

The MTD will be defined as the highest dose level at which no more than 1 patient of a maximum of 6 patients experienced an IMP-related DLT.

The patient population evaluable for MTD determination in the Dose Escalation Part will consist of all patients who receive at least 5 out of 6 weekly IV administrations of SAR440234 in DL1 and DL2, patients who receive at least 6 out of 7 IV administrations of SAR440234 in DL  $\geq$ 3, and patients who discontinue the IMP before completion of Cycle 1 because of a DLT.

A patient who discontinues the IMP before the end of the DLT observation period or does not receive the planned dose for any reason other than DLT, will be replaced by enrolling another patient. The first 3 patients treated during the Dose Escalation Part of TED15138 will be replaced. Another 3 patients will be enrolled in DL1 and the trial will proceed according to the 3+3 design.

The dose level below the MAD will be considered the preliminary MTD, providing DLTs are observed in fewer than 2 of 6 treated patients (or fewer than one-third if more than 6 patients) at that dose level. Intermediate dose levels may be evaluated according to Study Committee recommendations. The MTD is generally the highest dose level at which at most 1 patient of a dose level cohort experiences a DLT.

Although the dose escalation process is guided by the safety evaluation during the DLT observation period, cumulative or irreversible toxicities observed in subsequent administrations should also be considered for the dose escalation and dose selection decisions (ie, smaller increases in dose, expansion of a given dose level, or an intermediate dose level), upon agreement between the participant Investigators and the Sponsor.

In the absence of an MTD, pharmacokinetic and pharmacodynamic parameters may help to define the recommended dose of SAR440234 to be tested in the expansion cohort part of the study.

### 6.4 RETREATMENT OF PATIENTS

Patients may continue treatment with the IMP as long as clinical benefit is possible, or until disease progression, unacceptable adverse reaction, patient's decision to stop the treatment, or other reason for discontinuation (Section 6.8.1). Details of the criteria to be followed for retreatment of patients following an AE or an interruption in treatment are provided in Section 6.5.

### 6.5 DOSE DELAYS/MODIFICATIONS

Whenever possible, treatment should be performed on the scheduled days. Doses to be given are those planned unless a dose modification is warranted due to AE. Dose delays, omissions and modifications in response to AEs are delineated in (Section 6.5.3 to Section 6.5.5) and summarized in Table 5 (infusion-related reactions), Table 6 (CRS), Table 7 (hematological AEs), Table 8 (bone marrow hypocellularity Grade 4), and Table 9 (other AEs). The reasons for dose delays or modifications should be documented.

# 6.5.1 Dose delays

If any infusion (excluding Day 4 infusion) cannot be made on the scheduled day, a time window of +1 or -1 day is allowed. Subsequent infusions should be administered according to the regular weekly schedule.

**Dose delay of \geq 3 days:** If the infusion is administered  $\geq 3$  days later than planned, dosing must restart with the lead-in dose (Table 4).

If a Day 4 infusion cannot be made on the scheduled day: The infusion will be made on the next possible day, keeping a 4-day interval before the next infusion. If the infusion cannot be administered within 10 days of the last infusion, dosing must restart with the lead-in dose (Table 4).

#### 6.5.2 Dose modifications

When more than 1 AE is present, treatment modifications will be in accordance with the guidelines for the most severe AE.

Dose modifications, if required, will be a reduction of 1 step (Table 4) from the last administered dose. For example, if the last administered dose was (Step 5), a 1 step dose reduction would be to (Step 4). Otherwise, the lead-in dose will be based on the last administered dose.

Step Target Dose (ng/kg)

Lead-in Dosing When Restarting Treatment (if Applicable)

[figure not shown]
1
2
3
4
5
6
7
8
9
10

Table 4 - Definition of dose steps

IV=intravenous

11

The target dose is the dose that will be given every 7 days after lead-in dosing. When there is a dose delay of 2 days (ie, <10 days from the last infusion), the dose may be given without the lead-in dose.

If an AE requiring dose reduction and lead-in dosing occurs following the dose, the 1 ng/kg weekly dose will be administered.

If an AE requiring dose reduction occurs following the dose, the IMP will be discontinued.

After a safe and effective dose has been defined, individual patients who are still on study treatment at a different dose may be considered for treatment at another dose or schedule from which they were originally assigned, if this dose and schedule is thought to be safer and/or more effective, and the Sponsor and Investigator agree that it would be beneficial for the patient. If the dose exceeds the originally assigned dose, lead-in dosing will be administered.

Property of the Sanofi Group - strictly confidential

Page 59

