# 4.5.3 SAR440234 dose and regimen

A dose escalation single agent trial will be initiated in patients with R/R AML, HR-MDS, and B-ALL. This trial is intended to establish proof-of-concept for this drug, based on clinical, pharmacokinetic, and biomarker evaluation; to assess the safety and preliminary anti-leukemia activity of SAR440234; and to define the optimal dose of drug as a single agent.

Use of intra-patient dose escalation is proposed. This dosage strategy has already demonstrated its benefit in approved drugs, such as Blincyto®, with the same objective of cytokine release syndrome (CRS) mitigation. The strategy of intra-patient dose escalation is currently being used for other drugs under development.

In the first 2 dose levels (DL1 and DL2), SAR440234 will be administrated once weekly. After evaluation of the first 2 dose levels, a 2-step dosing increase in the first week of administration will be implemented to reach higher exposure in a shorter time frame.

A weekly schedule (bi-weekly during Cycle 1, Week 1 in DL  $\geq$ 3) will be evaluated with drug administration on Days 1, 4 (DL  $\geq$ 3 only), 8, 15, 22, 29, and 36 of a 6-week cycle that will be repeated, provided that the patient is achieving clinical benefit.

29-Aug-2019 Version number: 2

Cycles run consecutively so that Day 1 of each cycle is normally 7 days after the start of the last infusion in the previous cycle. If bone marrow hypocellularity Grade 4 or hematological toxicity Grade 3 or 4 is diagnosed, the interval between doses must be extended until toxicity is resolved. If the interval between doses is or exceeds 10 days, the treatment must be restarted with the lead-in doses appropriate for the selected dose level.

Systematic premedication with the corticosteroid, dexamethasone (two doses of 20 mg IV), and leukotriene inhibitor montelukast (one dose of 10 mg by mouth) are planned starting with the first dose of SAR440234 tested. Dexamethasone and/or tocilizumab will be used to treat Grade ≥2 CRS, as described below and in Section 6.7. Dexamethasone has been chosen because it penetrates the blood-brain barrier (20).

Use of intra-patient dose escalation is proposed. This dosage strategy has already demonstrated its benefit in approved drugs, such as Blincyto®, with the same objective of CRS mitigation. The strategy of intra-patient dose escalation is currently being used for other drugs under development, as well.

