To minimize the risk of severe CRS, an intra-patient dose escalation in Cycle 1 is proposed, as shown in Table 1. Lead-in doses include the first 2 doses in DL1 and DL2 (ie, Week 1 and Week 2 administered doses), the first 3 doses in DL3 to DL5, and the first 4 doses in DL6 to DL8. After the lead-in doses, each patient will receive a fixed dose until the end of treatment, unless the dose needs to be decreased for safety reasons. DL1 to DL8 will achieve a range of lead-in doses from and a range of final doses from During each cycle, pharmacokinetic and pharmacodynamic data will be collected that will be used, together with acute safety monitoring, in both the Dose Escalation and Expansion Parts.

Cycle 1 (doses in ng/kg) **Dose Level** Week 1 Week 2 Week 3 Week 4 Week 5 Week 6 Day 15 Day 29 Day 36 Day 1 Day 4 Day 8 Day 22 DL1 DL2 DL3 DL4 DL5 DL6 DL7

Table 1 - Intra-patient dose escalation: Cycle 1

DL=dose level

DL8

For subsequent cycles, patients will maintain the maximum weekly dose that they achieved in Cycle 1, as shown in Table 2.

Table 2 - Patient dosing after Cycle 1

			Cycle ≥2 (do	ses in ng/kg)		
Dose Level	Week 1	Week 2	Week 3	Week 4	Week 5	Week 6
DL1						
DL2						
DL3						
DL4						
DL5						
DL6						
DL7						
DL8						

DL=dose level

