### Grade 2:

- If the AE is resolved before the time of the next scheduled infusion, or within ≤10 days after the last infusion, treatment will continue without change after recovery.
- If the AE is resolved >10 days after the last infusion, omit 1 dose. After recovery, treatment will restart with the lead-in dose (Section 6.5.2) as appropriate to achieve the same step that was administered prior to the onset of the AE.
- If the patient experiences a third episode of the same AE, the study treatment will be permanently discontinued.

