#### Grade 4:

- The next infusion will be omitted.
- If the AE resolves in ≤14 days after the last infusion, if there is perceived benefit, and the Investigator and Sponsor agree, treatment will restart with the lead-in dose. Dose reduction by 1 step will be applied.
- If the AE is not resolved in ≤14 days after the last infusion, treatment will be permanently discontinued.
- If the patient experiences a second episode of the same AE, the study treatment will be permanently discontinued.

Guidelines for the resumption of treatment following treatment interruption secondary to AEs other than hematological AEs, CRS, or infusion-related reactions are provided in Table 9.

Table 9 - Dose delay and dose modification for adverse events not including hematological adverse events, cytokine release syndrome, or infusion-related reactions

Grade	Condition	Dur	ation of adverse e	vent	Second	Third
	to Continue Treatment	Resolved in <10 days after last infusion	Resolved in 10 to 14 days after last infusion	Persisting >14 days after last infusion	Episode	Episode
1	Not applicable		No change		No change	No change
2	Recovery to Baseline or Grade ≤1	Administer as planned on recovery with dose as planned.	Omit 1 dose Restart after AE resolved. Treatment will restart with the lead-in dose. May escalate to planned dose level.	Omit 1 dose. Restart after AE resolved. Treatment will restart with the lead-in dose. May escalate to planned dose level.	Allowed. Same recommend- ation as for first episode.	Permanent discontinua- tion a
3	Recovery to Baseline or Grade ≤1	Administer as planned on recovery. Dose reduction by 1 step.	Omit 1 dose. Restart after AE resolved. Dose reduction by 1 step and treatment will restart with the lead-in dose. Do not escalate past target dose.	Permanent discontinuation a	Permanent discontinua- tion a	Not applicable
4	Recovery to Baseline or Grade ≤1	Restart after AE re clinical benefit. Tre with dose reductio the lead-in dose. I	1 dose. solved if evidence of atment restart will be on by 1 step and with Do not escalate past et dose.	Permanent discontinuation a	Permanent discontinua- tion a	Not applicable

a If permanent discontinuation is mandated but there is evidence of clinical benefit and the AE has resolved, study treatment may continue if the Investigator and the Sponsor agree

AE=adverse event

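### Dose Escalation Part: two rules set the dose for later cycles (Cycle 1 maximum or last dose given), and they differ by 1 step for a patient reduced for toxicity in Cycle 1

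*Protocol*

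**What the plan says.** **Dose in later cycles.** Protocol 6.2.1, introducing Table 2, says that "patients will maintain the maximum weekly dose that they achieved in Cycle 1"; the Clinical Trial Summary (Dose Escalation Part) repeats this. Protocol 6.2.2 (Study continuation) and the matching paragraph of the Summary instead make the dose in each later cycle the final one of the cycle before.

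**Reductions.** Section 6.5.2 defines a reduction as 1 step in Table 4, counted from the dose last given. For restarts without a reduction it adds: "Otherwise, the lead-in dose will be based on the last administered dose". Section 6.5 opens with the general rule "Doses to be given are those planned unless a dose modification is warranted due to AE". In 6.2.1, the dose after lead-in is fixed unless safety requires a decrease.

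**Grade 2 non-hematological AE that resolves more than 10 days after the last infusion.** The 6.5.5 text restarts with lead-in "as appropriate to achieve the same step that was administered prior to the onset of the AE". The Grade 2 row of Table 9, for the same event, says "May escalate to planned dose level".

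**Gap of 10 days or more.** Section 4.5.3 says "the treatment must be restarted with the lead-in doses appropriate for the selected dose level", and 6.2.2 says "the next infusion must start with the lead-in doses appropriate for the selected dose level". Sections 6.5.1 and 6.5.2 point to Table 4.

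**The concern.** The two later-cycle rules give one answer for a patient whose dose never fell. They give two answers for a patient reduced for toxicity during Cycle 1: the maximum is the dose before the reduction, and the last dose is the reduced one. A site that follows 6.2.1 could return the patient to a dose already judged too high for that patient, while a site that follows 6.2.2 would not. In a first-in-human T-cell engager trial, two patients with the same history should not receive different doses because their sites read different sections. The Grade 2 wording raises the same question on a smaller scale.

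**Working it through.** The plan has no figure to reproduce. The check traces one patient through the rules. Write T for the final dose of the patient's assigned level and T−1 for the dose one Table 4 step lower. The step values are blacked out.

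**Can such a patient exist?** Take DL1 or DL2, with infusions on Days 1, 8, 15, 22, 29 and 36, of which the first two are lead-in (6.2.1).

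1. Days 15 and 22 are given at T.
2. Drug-related Grade 4 neutropenia, not present at baseline, begins after Day 22 and recovers to baseline or Grade 1 or less before Day 29.
3. Section 6.5.4 and Table 7 then require a 1-step reduction, so Days 29 and 36 are given at T−1.
4. The event lasts at most 29 − 22 = 7 days. The neutrophil DLT criterion in 6.2.1 requires non-recovery within 14 days, so it is not met.
5. Without a DLT, 6.7.5 lets Cycle 2 begin on Day 43. The interval is 43 − 36 = 7 days, so the 10-day restart rule is not triggered and only the later-cycle rules are in play.

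**What does each rule give?**

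| Rule | Patient above | Patient never reduced |
|---|---|---|
| Cycle 1 maximum (6.2.1; Summary) | T | T |
| Last dose of previous cycle (6.2.2; Summary) | T−1 | T |
| Difference | 1 step | 0 |

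Cycle 2 has 6 weekly infusions (Days 1, 8, 15, 22, 29, 36), so the 1-step difference runs for up to 6 infusions in that cycle. In the protocol's own example of a step (5 to 4), one rule gives Step 5 and the other Step 4.

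**Grade 2 AE resolved after more than 10 days.** Suppose the same patient, now at T−1, has such an event.

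- 6.5.5 text: back to the step given before the AE, T−1.
- Table 9: up to the planned dose level. If *planned* means the assigned level, this is T; if it means the current plan, T−1.
- Difference: 1 step or none, depending on that word.

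For a patient at T who was never reduced, both give T. For one still in Cycle 1 lead-in, the two can be read in sequence: regain the step, then resume the planned escalation. The conflict therefore matters only after an earlier reduction.

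**Selected dose level.** The term is not defined. If it means the patient's current step, 4.5.3 and 6.2.2 agree with Table 4. If it means the assigned level, the lead-in could be the one for T rather than T−1. The values in Tables 1 and 4 are blacked out, so whether adjacent steps have different lead-ins cannot be seen. This shows a difference in wording and no demonstrated difference in dose.

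**The case against.** The strongest reply is that the protocol already sends these patients to Section 6.5. Section 6.2.2 refers retreatment criteria there, 6.4 does the same after an AE or interruption, and 6.7.5 does so for the start of next infusions from Cycle 2 in Dose Escalation. Within 6.5, planned doses yield to AE modifications, and reductions are counted from the dose last given. The 6.2.1 paragraph before the Cycle 1 maximum sentence allows decreases for safety, and Table 2 is a default schedule by dose level. Several table cells also forbid going past the target dose. On Grade 2, Section 6.5 describes its text as setting the rules and its tables as summaries, and the Table 9 wording is permissive.

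Much of this stands: keeping the reduction is the more likely reading. It does not close the gap. Section 6.5 does not set the dose for the next cycle or say that a reduction lasts. The Cycle 1 maximum sentence carries no exception of its own. The Table 7 cell that applies in the worked case (resolved within 10 days) has no cap, and Table 9, inside 6.5, still departs from its own text.

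A reader might infer that the protocol orders re-escalation after toxicity. It does not; it leaves two rules standing without saying which prevails. A reader might also extend the point to the Expansion Part. The conflicting later-cycle sentences are Dose Escalation text, and 6.7.5 sends Expansion dosing to 6.5 from Cycle 1, so that extension is unsupported.

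**Conclusion.** The inconsistency is real and minor. In the Dose Escalation Part, a patient reduced from the target dose in Cycle 1 without a DLT has two stated Cycle 2 doses, 1 step apart, for up to 6 infusions; one of them undoes the reduction. The Grade 2 conflict between 6.5.5 and Table 9 is secondary and needs both an earlier reduction and *planned* read as the assigned level.

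The worked case assumes drug-related neutropenia, because 6.5.4 exempts cytopenias due to the disease or present at baseline. It also assumes that no other DLT criterion applies, including the one left to investigator and sponsor judgement. Such patients may be few; the documents give no basis for a frequency, and the blacked-out steps rule out a figure in ng/kg. Patients never reduced are unaffected.

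It would be tempting to add that the SAP's relative dose intensity is compromised. SAP 4.7.1.2 takes the intended dose from the CRF, which is not among the documents, so no error can be shown there. Nor do the documents show that the *selected dose level* wording changes any dose.

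**What to change.** 1. In 6.2.1 and the matching Summary sentence, replace the Cycle 1 maximum rule with: *patients will continue the last weekly dose given in the previous cycle; a dose reduced for toxicity is not re-escalated, except under the Sponsor- and Investigator-agreed change in 6.5.2*.
2. In the Grade 2 cells of Table 9, allow escalation only to *the planned dose level less any steps already removed for toxicity*.
3. In 4.5.3 and 6.2.2, replace *selected dose level* with a reference to the Table 4 lead-in for the patient's current step, including any reduction.

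The drafting should make clear that completing a restart lead-in up to the current step is not re-escalation. How far a patient reduced during Cycle 1 lead-in may later climb is a clinical decision that the protocol does not settle, and this change should not settle it by wording.

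The cost is wording changes in an amendment, with no extra patients or procedures. The SAP (4.3, 4.9) records early termination, so the practical value is limited to any patient still on treatment and to reuse of this text.

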# 6.5.3 Dose delay/modification for cytokine release syndrome and infusion-related reactions

Infusion-related reactions and CRS will be graded according to the 2014 NCI Consensus Guidelines (Appendix H). Recovery is defined as resolution to Grade 1 or less. CRS-like symptoms or signs that occur during infusion will be referred to as infusion-related reactions, while CRS-symptoms or signs that develop or persist after the infusion ends will be referred to as CRS. The patient's temperature, heart rate, blood pressure, oxygen saturation, and respiratory rate will be assessed every 30 minutes during the infusion. If clinical signs of an **infusion-related reaction Grade 1** develop, the infusion will be interrupted, and the patient will be treated with acetaminophen, diphenhydramine, and ranitidine, or similar agents. If the reaction remains at Grade 1 or less, the infusion will resume at 50% of the previous rate after up to 60 minutes of interruption. Up-titration of the rate may be attempted according to Section 8.1.2, provided that the AE remains Grade ≤1. If more than 60 minutes of interruption are required, the AE will be treated as for a Grade 2 infusion-related reaction.

If the **infusion-related reaction is Grade** ≥2, interrupt the infusion and treat the reaction. For Grade 2 infusion reactions, if the AE improves to Grade 1 or less within 48 hours, retreatment will be reattempted on the next scheduled day without a dose escalation, following premedication with dexamethasone, montelukast, acetaminophen, diphenhydramine, and ranitidine, or similar agents. If tolerated well, dose escalation (if planned) may resume with the next dose. If the infusion-related reaction persists for >48 hours, it will be managed as for a Grade 3 infusion-related reaction.

For **Grade 3 or Grade 4 infusion-related reactions**, interrupt the infusion and treat the reaction. The next dose will be omitted. After the AE resolves, treatment will restart on the next subsequent scheduled dosing day with additional premedication. Dose reduction by 1 step must be applied (Table 4). Treatment will restart with the lead-in dose.

For CRS Grade 1, no dose modifications or delays are required.

For CRS Grade 2 that resolves within 48 hours, the next dose should be given on schedule, but without a dose escalation. For CRS Grade 2 that persists for >48 hours or is present <48 hours before the next dose is scheduled, or a first episode of CRS Grade 3, the next dose will be omitted. After resolution of the AE, treatment will resume with the lead-in dose and a 1-step dose reduction. For CRS Grade 3 that fails to resolve to \(\leq\)Grade 1 within 72 hours, SAR440234 will be permanently discontinued. For a second or subsequent episode of CRS Grade 3, SAR440234 will be permanently discontinued. If CRS Grade >2 persists for >14 days after the last infusion, SAR440234 will be permanently discontinued.

For **CRS Grade 4**, the SAR440234 infusion must be stopped; no re-start is allowed. Treatment must be permanently discontinued.

Guidelines for the resumption of treatment and dose modification following treatment interruptions are provided in Table 5 (secondary to infusion-related reactions) and Table 6 (secondary to CRS).

Table 5 - Recommendations for resumption of treatment and dose modification following infusion-related reactions during SAR440234 infusion

Grade a	During SAR440234 Infusion (Infusion-related reaction)
1	Interrupt infusion and treat reaction, then resume the SAR440234 infusion at 50% of the rate previously achieved, and increase per Section 8.1.2, provided the event remains at Grade 1 or below. If AE requires interruption for >1 hour, treat as for Grade 2 event.
2	Interrupt infusion and treat reaction, then administer next dose on the next scheduled day without a dose escalation, but with additional premedication, provided AE has resolved within 48 hours. If tolerated well, dose escalation (if planned) may resume with subsequent doses.
	If AE persists for >48 hours, treat as for Grade 3 event.
3 or 4	Interrupt infusion and treat reaction. Omit next dose.
	After AE resolved, restart treatment on the next scheduled dosing day with additional premedication. Dose reduction by 1 step must be applied (Table 4). Treatment will restart with the lead-in dose.
	The reaction is a DLT if CRS occurs during Cycle 1.

a Grade of CRS according to the 2014 National Cancer Institute Consensus Guidelines (Appendix H) AE=adverse event, DLT=dose-limiting toxicity

Table 6 - Recommendations for resumption of treatment and dose modification following cytokine release syndrome after SAR440234 infusion is completed

Grade a	After SAR440234	Infusion completed			
	Duration of event <48 hours and event resolved >48 hours before next dose is due	Duration of event >48 hours and/or persistent <48 hours before next dose is due			
1	Administer the next dose when planned and escalate the dose (if planned).				
2	Administer the next dose when planned, but do	Omit next dose.			
	not escalate next dose. If tolerated well, dose escalation may resume subsequently.	After AE resolved, restart treatment. Dose reduction by 1 step must be applied (Table 4). Treatment will restart with the lead-in dose.			
		The reaction is a DLT if CRS occurs during Cycle 1.			
		If CRS Grade >2 persists for >14 days after the last infusion, SAR440234 will be permanently discontinued.			
3	Omit ne	ext dose.			
	After AE resolved, restart treatment. Dose reduction by 1 step must be applied (Table 4). Treatment w restart with the lead-in dose. Do not escalate past the target dose.				
	The reaction is a DLT if CRS occurs during Cycle 1				
		or if it recurs again, treatment will be permanently ntinued			
4	Permanent d	iscontinuation.			

a Grade of CRS according to the 2014 National Cancer Institute Consensus Guidelines (Appendix H) AE=adverse event, CRS=cytokine release syndrome, DLT=dose-limiting toxicity

